10.2. Urine Pharmacokinetics

10.2.1. Urine pharmacokinetic Concentrations

Pooled urine samples to assess urine PB2452, ticagrelor and TAM concentrations will be collected over the following intervals: before dosing (within 60 minutes prior to the first ticagrelor dose on Day -2) and 0 to 6, 6 to 12, and 12 to 24 hours post dose. In patients receiving a 6th dose of ticagrelor, pooled urine samples to assess urine ticagrelor and TAM concentrations will be collected over the following intervals after the 6th ticagrelor dose: 0 to 6, 6 to 12, 12 to 24 hours post dose.

For each analyte, urine concentration and volume data will be listed by collection interval for each subject.

10.2.2. Urine Parameters

The following PK parameters for PB2452, ticagrelor and TAM concentrations in urine will be calculated for Day 1 whenever data permit:

Parameter	Description
Ae ₂₄	Total amount of drug excreted in urine from time 0 to 24 hours post-dose.
Ae _{t1-t2}	Ae from time t1 to t2 hours where the values of t1 to t2 are 0 to 6, 6 to 12, and 12 to 24 post-dose.
Fe ₂₄	Fraction excreted in urine from 0 to 24 hours after dosing (ticagrelor only).
CLR ₂₄	Renal clearance, calculated as Ae ₂₄ /AUC ₀₋₂₄

Additional urine PK parameters may be calculated, as necessary. Urine parameters will be listed by subject and summarized for each dose level using descriptive statistics (number of subjects, mean, SD, CV, median, minimum, and maximum).

11. Pharmacodynamics

The PD population will be used for all PD analysis tables and figures, except otherwise noted. All tables and listings for PD will be done for both Part A and Part B of the study, separately.

11.1. Pharmacodynamic Data

Blood samples for PD analysis will be collected from subjects at the following time points: Day -3, before dosing (within 60 minutes prior to 1st ticagrelor dose on Day -2) and again before dosing (within 10 minutes prior to the initiation of the study drug infusion [Hour 0]), and up to 48 hours after the initiation of study drug infusion. Collection time points for each cohort will be specified in a Dosing Memo from Sponsor to PPD prior to initiation of each cohort. The

sampling schedule for a given cohort may differ from that of other cohorts to accommodate various infusion durations that may be examined in the protocol in order to fully characterize the PK/PD profile.

Specific collection times were identical for all 3 cohorts: Day -3, Day -2 (up to 60 minutes prior to 1st ticagrelor dose) and Hour 0 (up to 10 minutes prior to PB2452 infusion), 5 minutes, 0.25, 0.5, 1, 2, 4, 8, 12, 20, 24, 36 and 48 hours after initiation of PB2452 or placebo infusion

Platelet aggregation will be assessed using the VerifyNow, LTA and VASP assays. The results for the VerifyNow assay will be expressed as PRU and %baseline PRU, which will be calculated from the platelet aggregation-time profile for each sampling time point. The results of platelet aggregation from the LTA assay using 5 μ M ADP and 20 μ M ADP will be expressed as maximal-extent aggregation (MA), %baseline MA, final-extent aggregation (FA) and %baseline FA, which will be calculated from the platelet aggregation-time profile for each sampling time point. The results of platelet aggregation from the LTA assay using agonists 1.6 mM AA and 15 μ M TRAP will be included in SDTM PD dataset only and not included in tables, listings or figures. Similarly, PD results from the VASP assay will be expressed as PRI and %baseline PRI, which will be calculated from the platelet aggregation-time profile for each sampling time point.

Blood drawn for LTA PD assessments will be further processed for testing soluble and surface P-selectin/CD62p after completion of LTA, as per instructions. All LTA timepoints will have samples processed for testing however only the time points as defined below are planned for testing P-selectin. The remaining samples will be stored, as per their stability profiles, for future testing if needed to help elucidate the results. The sampling schedule for P-selectin for subsequent cohorts will be specified in a Dosing Memo provided by Sponsor to PPD prior to initiation of each cohort.

Specific P-selectin collection times were: Day -2 (up to 60 minutes prior to first ticagrelor dose), Hour 0 (up to 10 minutes prior to PB2452 infusion), 12 and 24 hours.

Pharmacodynamic data will be listed by subject and ADA status and summarized for each treatment group for each time point using descriptive statistics (number of subjects, mean, SD, median, minimum, and maximum). Mean PD data versus scheduled time profiles will be presented graphically. Biomarker data (P-selectin) will be listed and summarized by each cohort for each time point using descriptive statistics (number of subjects, mean, SD, median, minimum, and maximum).

Scatter plots of PD data versus total and unbound PB2452 plasma concentrations will be prepared for all cohorts, as appropriate. A box plot of PD data versus sampling time point will be prepared for each dose level.

Scatter plots of CrCl versus total and unbound ticagrelor and TAM plasma concentrations will be prepared for all cohorts, as appropriate.

Correlation between VerifyNow assay, LTA assay, and VASP assay will be investigated graphically. Scatter plots of individual subject PRU versus MA (5 μ M ADP and 20 μ M ADP),

PRU versus PRI, and MA (5 μ M ADP and 20 μ M ADP) versus PRI will be plotted, and the correlation coefficient r (Spearman's rank correlation coefficient) and p-value will be displayed.

11.2. 10.2 Pharmacodynamic Parameters

Pharmacodynamic parameters will be calculated using actual timepoints using SAS[®] Version 9.4 or higher. Missing PD values will be treated as missing for PD parameter calculation.

The following PD parameters will be calculated using %baseline/actual PRU data from the VerifyNow assay.

Day 1 parameters following 5th ticagrelor dose	
APRUMax	Maximal actual PRU
APRUMax4h	Maximal actual PRU within 4 h
PRUmax	Maximal percent of baseline PRU
TPRUMax	Time to maximal actual PRU
TPRU180	Time to 180 or higher actual PRU, calculated as the first observed time point (no extrapolation) when the actual PRU reaches 180 or above
TPRU200	Time to 200 or higher actual PRU, calculated as the first observed time point (no extrapolation) when the actual PRU reaches 200 or above
TPRU220	Time to 220 or higher actual PRU, calculated as the first observed time point (no extrapolation) when the actual PRU reaches 220 or above
TPRU60%	Time to 60% of baseline PRU, calculated as the first observed time point (no extrapolation) when %baseline PRU reaches 60% or above
TPRU80%	Time to 80% of baseline PRU, calculated as the first observed time point (no extrapolation) when %baseline PRU reaches 80% or above
TPRU90%	Time to 90% of baseline PRU, calculated as the first observed time point (no extrapolation) when %baseline PRU reaches 90% or above

The following PD parameters will be calculated using %baseline/actual MA and FA data, as appropriate, from the LTA assay for both the 5 μ M and 20 μ M ADP conditions.

Day 1 parameters following 5th ticagrelor dose	
APAmx	Maximal actual platelet aggregation
APAmx4h	Maximal actual platelet aggregation within 4 h
PAmax	Maximal percent of baseline platelet aggregation
TPAmx	Time to maximal actual platelet aggregation
TPA60%	Time to 60% of baseline platelet aggregation, calculated as the first observed time point (no extrapolation) when %baseline platelet aggregation reaches 60% or above
TPA80%	Time to 80% of baseline platelet aggregation, calculated as the first observed time point (no extrapolation) when %baseline platelet aggregation reaches 80% or above

TPA90%	Time to 90% of baseline platelet aggregation, calculated as the first observed time point (no extrapolation) when %baseline platelet aggregation reaches 90% or above
--------	---

The following PD parameters will be calculated using %baseline/actual PRI data from the VASP assay.

Day 1 parameters following 5th ticagrelor dose	
APRImax	Maximal actual PRI
APRImax4h	Maximal actual PRU within 4 h
PRImax	Maximal percent of baseline PRI
TPRImax	Time to maximal actual PRI
TPRI60%	Time to 60% of baseline PRI, calculated as the first observed time point (no extrapolation) when %baseline PRI reaches 60% or above
TPRI80%	Time to 80% of baseline PRI, calculated as the first observed time point (no extrapolation) when %baseline PRI reaches 80% or above
TPRI90%	Time to 90% of baseline PRI, calculated as the first observed time point (no extrapolation) when %baseline PRI reaches 90% or above

Additional PD parameters may be calculated, as necessary. Pharmacodynamic parameters will be listed by subject and summarized for each cohort using descriptive statistics (number of subjects, mean, SD, median, minimum, and maximum). Number and percent of subjects achieving 60%, 80%, and 90% of reversal in PRU, LTA, and PRI within 30 minutes or 4 h will be summarized.

12. Interim Analysis

There is no interim analysis planned for this study.

13. Changes in the Planned Analysis

There is no change in the SAP compared to the protocol

14. References

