### **1.1.3 Benefit/Risk Assessment**

The first in human study of PB2452 in healthy volunteers (PB2452-PT-CL-0001) demonstrated that PB2452 appears to be generally safe and well tolerated when administered intravenously across a dose range of 0.1-18 g. The healthy volunteers who were 18-50 years in age were not expected to nor received any benefit from administration of PB2452. Platelet function analyses showed that PB2452 delivered immediate and sustained reversal of ticagrelor, occurring as early as 5 minutes after initiation of PB2452 infusions and lasting for 20-24 hours. Rapid and sustained ticagrelor reversal by PB2452 may provide clinically significant benefit in patients taking ticagrelor who experience serious bleeding or require urgent surgical procedures by supporting rapid hemostasis or prevention of procedure-related bleeding.

Although treatment emergent adverse events associated with PB2452 in the Phase 1 study were mostly mild and infrequent with no infusion-related or hypersensitivity reactions observed, in the older and elderly subjects in this Phase 2A study, there remain potential risks of infusion-related reactions (IRRs), infusion site reactions, and hypersensitivity-type reactions which can result from exposure to recombinant protein drugs administered intravenously (IV). These risks may be mitigated by predefined exclusion criteria and by close monitoring during and after administration. Risks may also be mitigated by premedication prior to receiving PB2452 which will be implemented if a study subject develops a Grade  $\geq 2$  IRR.

The older and elderly subjects in this study will be administered dual anti-platelet therapy with ASA and ticagrelor which carries a risk of bleeding. The bleeding risk in study subjects is considered very low because the duration of dual antiplatelet therapy is only 48 hours. Among those patients taking ticagrelor for therapeutic benefit, the potential risk of disease-related thrombosis upon reversal of the antiplatelet effect of ticagrelor will be evaluated in future clinical studies and by thorough monitoring of hemostasis parameters. In the current study, three platelet function assays and multiple platelet agonists will be used to monitor platelet function which will demonstrate both the reversal profile of PB2452 and also a potential prothrombotic rebound increase in platelet function. The risk of a platelet rebound effect is considered low and was not observed in the Phase 1 study.

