### **3.6.3 Statistical Analysis**

Details concerning all statistical analyses will be described in a separate Statistical Analysis Plan (SAP). All data collected during the study will be presented in Data Listings.

Data from subjects excluded from an analysis population will be presented in the Data Listings but will not be included in the calculation of summary statistics.

Data from subjects who receive placebo will be pooled across cohorts for all presentations.

For categorical variables, frequencies and percentages will be presented. Continuous variables will be summarized using descriptive statistics (number of subjects, mean, median, standard deviation [SD], minimum, and maximum).

Demographic and baseline characteristics will be summarized. The number of subjects who enroll in the study and the number and percentage of subjects who complete the study will be presented. Frequency and percentage of subjects who withdraw or discontinue from the study, and the reason for withdrawal or discontinuation, will also be summarized.

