3.2.3. Pharmacodynamic Endpoints

Pharmacodynamic data and parameters will be generated from PRU, LTA and PRI assays:

VerifyNow®P2Y₁₂:

- PRU at each assessment point
- Percent of reversal (%baseline) in ticagrelor antiplatelet activity by PRU at each assessment point
- Maximum PRU
- Maximal percent of baseline PRU
- Time to maximum PRU
- Maximum PRU within 4 hours
- Time to ≥ 180 PRU
- Time to ≥ 200 PRU
- Time to ≥ 220 PRU
- Time to 60%, 80%, and 90% of reversal in PRU

LTA:

- The maximum and final extent of aggregation for up to 4 platelet agonists (20 μ M adenosine diphosphate [ADP], 5 μ M ADP, 1.6 mM arachidonic acid [AA], and 15 μ M thrombin receptor activating peptide [TRAP]), will be recorded at each assessment point.
- Percent of reversal (%baseline) in ticagrelor antiplatelet aggregation
- Maximum platelet aggregation
- Maximum percent of baseline platelet aggregation
- Time to maximum platelet aggregation
- Maximum platelet aggregation within 4 hours
- Time to 60%, 80%, and 90% of reversal in platelet aggregation

VASP by ELISA:

- PRI at each assessment point
- Percent of reversal (%baseline) in PRI at each assessment point
- Maximum PRI
- Maximum percent of baseline PRI
- Time to maximum PRI
- Maximum PRI within 4 hours
- Time to 60%, 80%, and 90% of reversal in PRI
- Time to minimum PRI

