Descriptive statistics for continuous variables will include number of subjects, mean, standard deviation (SD), median, minimum, and maximum, unless otherwise noted. Minimum and maximum will be presented to the same number of decimal places as the raw data, mean and median will be presented to one more decimal place than the raw data, and SD will be presented to two more decimal places than the raw data, unless otherwise specified.

Frequency and percentage will be calculated for categorical variables. Percentages will be presented with 1 decimal place, and if the value is less than 0.1, then “<0.1” will be displayed.

All data will be provided in by-subject listings.

For summary of safety assessments, if there are repeated measurements at a time point, the original measurement at that time point will be used in the summary tables. If the original measurement is missing, the next available measurement at that time point will be used in the summary tables.

Baseline will be defined as the last nonmissing assessment before study drug (PB2452 or matching placebo) administration.

Unscheduled results will not be included in the summary tables except for determining Baseline but will be presented in data listings.

Unless otherwise stated, the following treatment groups will be used in the summaries, where C denotes Cohort:

- 18 g PB2452 (C1)
- 18 g PB2452 (C2)
- 36 mg PB2452 (C3)
- Placebo
- All PB2452 (for safety analyses only)
- All Subjects (for safety analyses only)

Outputs will be provided for Part A and Part B, separately.

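### SAP 11.1 keeps arachidonic-acid and TRAP aggregation out of all outputs, against the rule that all data are listed, so the non-ADP part of the multi-agonist rebound check goes unreported

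*SAP*

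**What the plan says.** Section 1.1.3 (Benefit/Risk Assessment) of both the Part A and Part B protocols says that "three platelet function assays and multiple platelet agonists will be used to monitor platelet function". The stated purpose is to show the reversal profile and "also a potential prothrombotic rebound increase in platelet function". Neither protocol says in its body which agonists are meant; AA and TRAP appear only in the abbreviation lists.

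The SAP supplies the agonists. Section 3.2.3 makes this an LTA endpoint: "The maximum and final extent of aggregation for up to 4 platelet agonists", namely 20 µM ADP, 5 µM ADP, 1.6 mM AA and 15 µM TRAP, recorded at each assessment point.

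SAP 11.1 then splits the set. The two ADP conditions are reported as maximal-extent aggregation (MA) and final-extent aggregation (FA), each as an actual value and as %baseline. The AA and TRAP results "will be included in SDTM PD dataset only and not included in tables, listings or figures". The LTA parameters in SAP 11.2 and the between-assay scatter plots in SAP 11.1 also use ADP only.

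Three other statements bear on this:
- SAP section 4 (General Statistical Considerations): "All data will be provided in by-subject listings".
- Protocol 3.6.3 (Statistical Analysis), in both parts: "All data collected during the study will be presented in Data Listings".
- SAP section 13 (Changes in the Planned Analysis): "There is no change in the SAP compared to the protocol".

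**The concern.** An endpoint named in one section of the SAP is denied every output in another, and no reason is given. The endpoint also belongs to a check that the protocols cite when they weigh thrombotic risk.

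The reported functional readouts are the ones used to show reversal. Protocol 1.1.1 describes PB2452 as reversing ticagrelor's inhibition of ADP-induced aggregation. The primary and secondary objectives use the VerifyNow P2Y12 assay, LTA and PRI to measure ticagrelor's antiplatelet effect. If LTA is reported for ADP alone, a value above baseline is hard to interpret: it may belong to the pathway being restored, or it may be a general rise in platelet reactivity. AA and TRAP are the only non-ADP LTA agonists that the SAP names, so they are the aggregation data that could help to separate the two. A reader of the study report would not see them.

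**Working it through.** The plan states no figure to reproduce. The check compares the texts and counts what is left out.

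**Consistency of the reporting rules**

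| Source | AA and TRAP results |
|---|---|
| SAP 3.2.3 | Named as LTA endpoints, recorded at each assessment point |
| SAP 4 | Listed by subject (rule for all data) |
| Protocol 3.6.3, Parts A and B | Listed (rule for all collected data) |
| SAP 11.1 | Not tabulated, listed or plotted; kept in SDTM |
| SAP 13 | No departure from the protocol declared |

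SAP 11.1 cannot be reconciled with SAP 4 or with protocol 3.6.3. Since it departs from protocol 3.6.3, the statement in SAP 13 is also incorrect on this point. These conflicts need no inference about rebound.

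**Amount of LTA data affected**

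Inputs:
- Agonist conditions (SAP 3.2.3): 4, of which 2 (AA, TRAP) are withheld.
- Readouts per condition (SAP 3.2.3 and 11.1): 2 (MA and FA).
- Sampling times (SAP 11.1): Day -3, Day -2 and Hour 0, then 5 minutes, 0.25, 0.5, 1, 2, 4, 8, 12, 20, 24, 36 and 48 hours. That is 3 + 12 = 15.

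Planned LTA values per subject = 4 × 2 × 15 = 120.

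Withheld LTA values per subject = 2 × 2 × 15 = 60, or 60/120 = 50%.

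These are upper figures, because the SAP allows fewer than four agonists. By substance, reported LTA falls from three agonists (ADP, AA, TRAP) to one (ADP, at two concentrations).

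**What can still show a rise above baseline**

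- VerifyNow: PRU and %baseline PRU at each time, plus PRUmax ("Maximal percent of baseline PRU").
- LTA with 5 and 20 µM ADP: MA and FA, actual and %baseline, plus the maximal percent of baseline aggregation (PAmax).
- VASP: PRI and %baseline PRI, plus PRImax.
- P-selectin: SAP 11.1 specifies Day -2, Hour 0, 12 h and 24 h. That is 2 post-dose times against 12 for LTA, with none in the first hours and none at 36 or 48 h.

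The maxima and the %baseline profiles can exceed 100%, so they can reveal overshoot. The SAP defines no rebound parameter, threshold or summary for any of these measures.

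**The case against.** The strongest reply is that the rebound check largely survives. All three assays promised in protocol 1.1.3 are reported through 48 hours, with measures that can exceed baseline, and P-selectin is a reported marker of platelet activation. The AA and TRAP data are retained in SDTM, and the exclusion is written openly. SAP 3.2.3 counts the two ADP concentrations as separate agonists, so on the SAP's own count more than one agonist is still reported. Section 11.1 is also a specific provision, which would normally override the general listing rule in section 4.

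Much of this stands, and it rules out several stronger readings:

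- A reader might infer that rebound goes unreported altogether. It does not: the outputs set out above can show it. Only the non-ADP aggregation part is missing.
- A reader might infer that the data are lost. They remain in the SDTM dataset.
- A reader might take reactivity outside the ADP pathway to be a safety question that the protocol itself poses. Protocol 1.1.3 names no pathway or agonist, and the link to AA and TRAP comes through SAP 3.2.3. LTA is a secondary pharmacodynamic measure and is absent from the safety endpoints in protocol 2.2.1 and SAP 3.2.1. Protocol 1.1.3 also calls the rebound risk low and says that none was seen in Phase 1.
- A reader might call this selective reporting. The documents show an openly stated, unexplained exclusion and no evidence that it depends on results.

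The contradiction remains. A specific SAP clause may override a general SAP clause, but it does not remove the conflict with protocol 3.6.3, which SAP 13 says does not exist. P-selectin at two post-dose times does not replace agonist-induced aggregation at twelve. A sponsor might argue that AA is uninformative under aspirin in Part A. The SAP does not say so, and the argument would not cover TRAP in either part, or AA in Part B, where protocol 1.1.3 gives ticagrelor without aspirin.

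**Conclusion.** The point holds in a limited form. SAP 11.1 removes AA and TRAP aggregation from every table, listing and figure. That contradicts SAP 4 and protocol 3.6.3 in both parts, and SAP 13 does not declare it. The multiple-agonist check in protocol 1.1.3 then rests, as reported, on ADP-based LTA, PRU, PRI and P-selectin at 12 and 24 hours.

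The size is two of four LTA conditions, or up to 60 of 120 LTA values per subject, assuming that all four agonists are run at all 15 times.

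Two further assumptions matter. The first is that the agonists meant in protocol 1.1.3 are those named in SAP 3.2.3. The second is that %baseline is taken against the pre-ticagrelor value, as protocol 2.2.2 defines it for PRU. SAP 4's general definition of baseline is the last assessment before study drug. If that applied, values above 100% would not by themselves indicate rebound, and the remaining outputs would show less than is credited to them here.

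The change should be made, because it is cheap and restores the only non-ADP aggregation evidence. It would not settle the rebound question by itself, since no rebound criterion is defined for any assay.

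**What to change.** In SAP 11.1, delete the sentence that confines AA and TRAP results to the SDTM dataset. For Parts A and B, wherever these agonists were run:

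- list AA and TRAP MA and FA by subject;
- summarise actual and %baseline values descriptively by treatment group and time point, reusing the ADP shells and the same baseline as for ADP.

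At minimum, provide the by-subject listings, which resolves the conflict with SAP 4 and protocol 3.6.3. Then declare and justify in SAP 13 any summary that is still omitted, for example AA under aspirin in Part A.

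The cost is an edit to the SAP and a few more descriptive outputs. The results already go to SDTM, so no new sampling, assays or subjects are needed.

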The PK profile of PB2452 demonstrated that mean plasma concentrations of PB2452 rapidly declined following the end of infusion across all cohorts. In cohorts 1-3 when PB2452 was administered as a 30-minute intravenous infusion in the absence of ticagrelor, elimination appeared to be biphasic with half-life values ranging from 1.5 to 9.2 hours for the dose range 0.1 g to 1 g. In the presence and absence of ticagrelor, geometric mean observed maximum plasma concentration ( $C_{max}$ ) values and geometric mean area under the plasma concentration versus time curve (AUC) from time zero extrapolated to infinity ( $AUC_{0-\infty}$ ) values of total PB2452 appeared to increase in a dose-proportional manner. The inter-individual variability (geometric mean coefficient of variation [CV%]) for  $C_{max}$  and  $AUC_{0-\infty}$  was low, ranging from 4.8% to 28.9% across Cohorts 1-3. PB2452 appeared to increase mean total plasma concentrations of ticagrelor and TAM compared to placebo, and this effect was dependent on the dose of PB2452. Additionally, PB2452 increased the renal CL of ticagrelor and TAM in a dose-dependent manner.

The PD profile of PB2452 demonstrated that for subjects receiving steady-state ticagrelor, IV infusion of PB2452 (3 to 18 g) restored platelet activity to approximately 100% of baseline using multiple assays of platelet function. The onset of reversal was rapid, occurring at the first assessment of platelet function following initiation of PB2452 infusion (30 minutes in cohorts 4-6 and 5 minutes in cohorts 7-10). The duration of ticagrelor reversal appeared to be dependent on the total dose and infusion duration of PB2452.

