- To evaluate the effect of PB2452 on ticagrelor antiplatelet activity by measuring platelet aggregation with light transmittance aggregometry (LTA) and platelet reactivity index (PRI) with vasodilator-stimulated phosphoprotein (VASP) assay by enzyme-linked immunosorbent assay (ELISA), for each of Part A and B
- To evaluate the immunogenicity potential of PB2452, for each of Part A and B

2.3 Exploratory Objectives:

- To evaluate the effect of PB2452 on the PK profile of unbound ticagrelor and unbound TAM plasma concentrations, for each of Part A and B
- To investigate the effect of PB2452 vs matching placebo on circulating biomarkers of platelet activation, such as P-selectin, in subjects pretreated with ticagrelor + ASA, for each of Part A and B
- To examine the correlation between estimated creatinine clearance (CrCl) and the PK of ticagrelor and TAM, for each of Part A and B

3. Investigational Plan

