10.1.1. Plasma Pharmacokinetics Concentration

Throughout this document, the total MEDI2452 (PB2452) includes free MEDI2452 (PB2452), protein-bound MEDI2452 (PB2452), ticagrelor-complexed MEDI2452 (PB2452), and TAM-complexed MEDI2452 (PB2452). The unbound MEDI2452 (PB2452) includes free MEDI2452 (PB2452) and protein-bound MEDI2452 (PB2452). Similarly, total ticagrelor (or TAM) includes free ticagrelor (or TAM), protein bound ticagrelor (or TAM), and MEDI2452 (PB2452)-complexed ticagrelor (or TAM). The unbound ticagrelor (or TAM) includes free ticagrelor (or TAM).

Blood samples for PK analysis of total and unbound PB2452 concentration in plasma will be collected from all subjects at the following time points: before dosing (0 hour) and up to 28 days after initiation of the study drug (PB2452 or placebo) infusion. Collection time points for cohorts were be specified in a Dosing Memo from Sponsor prior to initiation of each cohort, and are provided below.

Collection times relative to the initiation of the study drug (PB2452 or placebo) infusion on Day 1 were: Hour 0 (up to 10 minutes prior to PB2452 infusion), 5 minutes, 0.25, 0.5, 1, 2, 4, 8, 12, 20, 24, 36, 48 hours, and 7 and 28 days post-dose.

Plasma samples for determining total and unbound concentrations of ticagrelor and its active metabolite TAM, will be collected at the following timepoints: before dosing (within 10 minutes prior to the initiation of the study drug infusion [Hour 0]), and up to 28 days following the initiation of PB2452 or placebo infusion on Day 1. Subjects will be administered the 5th ticagrelor dose two hours before the study drug infusion initiation on Day 1.

Specific collection times relative to the initiation of the study drug (PB2452 or placebo) infusion were: Hour 0 (up to 10 minutes prior to PB2452 infusion), 5 minutes, 0.25, 0.5, 1, 2, 4, 8, 12, 20, 24, 36, 48 hours, and 7 and 28 days post-dose.

Concentrations that are below the limit of quantification (BLQ) will be treated as zero for descriptive statistics. Mean BLQ concentrations will be presented as BLQ, and the SD and

coefficient of variation (CV) will be reported as not applicable. Missing concentrations will be excluded from the calculations.

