Ticagrelor/ TAM PK parameters:

Parameter	Description
C _{max}	Observed maximum plasma concentration
T _{max}	Time to reach the observed maximum plasma concentration
AUC _{0-t}	AUC from time 0 to the time of last quantifiable concentration (C _{last}); calculated using the linear-up/log-down trapezoidal rule
AUC _{0-inf}	AUC from time 0 extrapolated to infinity, calculated as AUC _{0-t} + C _{last} / λz , where C _{last} is the last quantifiable plasma drug concentration and λz is the terminal phase rate constant.
AUC ₀₋₂₄	AUC from time 0 to 24 hours post-dose; calculated using the linear-up/log-down trapezoidal rule
AUC ₀₋₄₈	AUC from time 0 to 48 hours post-dose; calculated using the linear-up/log-down trapezoidal rule
%AUCextrap	Percentage of AUC _{0-inf} due to extrapolation from the time for the last quantifiable concentration to infinity, calculated as (AUC _{0-inf} - AUC _{0-t}) / AUC _{0-inf} * 100
λz	Terminal phase rate constant, determined by linear regression of the terminal points of the log-linear plasma concentration-time curve. The λz will not be estimated if the terminal phase of the log-concentration-time profile does not exhibit a linear decline phase, or if the regression coefficient (Rsq) is less than 0.8.
Rsq	Regression coefficient for calculation of λz
$t_{1/2}$	Terminal elimination half-life, calculated as $t_{1/2} = \ln(2) / \lambda z$.

Additional PK parameters may be calculated, as necessary. Pharmacokinetic parameters will be listed by subject and summarized for each dose level using descriptive statistics (number of subjects, mean, SD, CV, median, minimum, and maximum), with the exception of %AUCextrap, λz and Rsq, which will be listed only. Geometric means will be reported for AUCs and C_{max}.

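### The exploratory objective asks for the correlation of creatinine clearance with ticagrelor and TAM PK, but the SAP plans only scatter plots against concentrations, with no coefficient, sampling time, treatment split or per-subject PK parameter

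*SAP*

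**What the plan says.** SAP 2.3 lists as an exploratory objective: "To examine the correlation between estimated creatinine clearance (CrCl) and the PK of ticagrelor and TAM, for each of Part A and B". Section 2.1 of the Part A and Part B protocols carries the same objective, and section 3.6.3 of each leaves the details of all analyses to the SAP.

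The SAP answers with one sentence in 11.1, within the pharmacodynamics section: "Scatter plots of CrCl versus total and unbound ticagrelor and TAM plasma concentrations will be prepared for all cohorts, as appropriate". Elsewhere in the SAP:

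- **Sampling (10.1.1).** Ticagrelor and TAM are measured at Hour 0 and then at "5 minutes, 0.25, 0.5, 1, 2, 4, 8, 12, 20, 24, 36, 48 hours, and 7 and 28 days post-dose".
- **Plasma parameters (10.1.2).** Cmax, AUC0-24, AUC0-48, half-life and others are derived for total and unbound ticagrelor and TAM. Their use is given as: "Pharmacokinetic parameters will be listed by subject and summarized for each dose level using descriptive statistics".
- **Urine parameters (10.2.2).** CLR24 is defined as "Renal clearance, calculated as" Ae24/AUC0-24.
- **Assay correlations (11.1, next paragraph).** For the scatter plots of one platelet assay against another, the Spearman "rank correlation coefficient) and p-value will be displayed".
- **Renal function (6.1).** It is summarised by GFR category among the demographics. The SAP gives no formula for CrCl and does not say which creatinine sample feeds it.

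**The concern.** The objective names a correlation with PK. The planned display gives no coefficient and uses single concentrations, not the exposure and clearance parameters that describe a subject's PK. CLR24 is the planned parameter most directly tied to renal function, and it is never set against CrCl.

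Two gaps in the sentence could make the plots hard to read. First, if all sampling times go on one plot, time since dosing drives much of the vertical spread and each subject contributes many points. Second, Part A protocol 1.1.2 reports from Phase 1 that "PB2452 increased the renal CL of ticagrelor and TAM in a dose-dependent manner", and that mean total ticagrelor and TAM concentrations appeared higher with PB2452 than with placebo. Points that do not distinguish PB2452 from placebo would therefore mix a treatment effect with any effect of renal function.

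At stake is whether the study report can answer this objective from a pre-specified analysis. No primary or secondary conclusion depends on it.

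**Working it through.** **1. No figure to reproduce.** SAP 4.1 gives no power basis for the sample size, and no correlation is stated for this objective.

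**2. Objective against plan.**

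| Needed to report a correlation with PK | Stated in the SAP? |
|---|---|
| CrCl formula and creatinine sample | No |
| PK quantity | Plasma concentration, no time named |
| Handling of repeated times | No |
| Treatment split for this plot | No; outputs are by Part (SAP 4) |
| Coefficient | No, though the assay pairs get one |

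**3. Number of points if times are pooled.** Sampling times are Hour 0, 12 times from 5 minutes to 48 hours, and Days 7 and 28: 1 + 12 + 2 = 15. A cohort of 8 to 12 (SAP 3.1) gives 8 × 15 = 120 to 12 × 15 = 180 points per analyte. Two cohorts of 12 in Part A give 24 × 15 = 360.

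**4. What pooling would do (illustrative).** The following assumptions are not in the documents:

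- log concentration falls linearly with a half-life of 8 or 12 h;
- between-subject SD is 0.4 and residual SD 0.2 on the log scale;
- the 13 times to 48 h are used;
- there is one CrCl value per subject and no treatment effect;
- each setting has 1,500 runs.

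Mean Spearman coefficient when the true subject-level correlation is -0.5:

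| Subjects | Half-life | All times pooled | Single time (4 h) | One AUC per subject |
|---|---|---|---|---|
| 12 | 8 h | -0.176 | -0.405 | -0.440 |
| 12 | 12 h | -0.215 | -0.400 | -0.453 |
| 24 | 8 h | -0.182 | -0.415 | -0.457 |
| 24 | 12 h | -0.223 | -0.420 | -0.459 |

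The pooled coefficient is 0.176/0.440 = 40% to 0.223/0.459 = 49% of the per-subject one. The AUC here runs over the simulated 48 hours, as a stand-in for any per-subject exposure measure.

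**5. What the available numbers can support.** SAP 3.3 records two cohorts in Part A and one in Part B. At 3:1:

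- Part A has 16 to 24 subjects, so 12 to 18 on PB2452 and 4 to 6 on placebo.
- Part B has up to 12 subjects, so up to 9 on PB2452 and at most 3 on placebo.

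An approximate 95% interval is tanh(atanh(r) ± 1.96/√(n − 3)), with atanh(0.5) = 0.549. This is the Fisher form, used as a guide for Spearman's coefficient.

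| Group | n | 1.96/√(n − 3) | Observed r | Interval |
|---|---|---|---|---|
| Placebo, Part A | 4 | 1.960 | 0.5 | -0.89 to 0.99 |
| Placebo, Part A | 6 | 1.132 | 0.5 | -0.52 to 0.93 |
| Placebo, Part B | 3 | undefined | – | none |
| PB2452, Part B | 9 | 0.800 | -0.5 | -0.87 to 0.25 |
| PB2452, Part A | 12 | 0.653 | -0.5 | -0.83 to 0.10 |
| PB2452, Part A | 18 | 0.506 | -0.5 | -0.78 to -0.04 |

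Placebo intervals are uninformative or do not exist. Those for PB2452 are wide but can be reported as descriptive.

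**The case against.** The strongest reply is that the SAP leaves details open but does not choose a wrong method. Several parts of that reply stand.

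- **Sampling times.** A reader might infer that every concentration from pre-dose to Day 28 goes on one plot. The sentence does not say so. Plots by scheduled time would satisfy it, with one concentration per subject on each. Pooling remains the likelier reading, because the wording matches that for PD data against PB2452 concentrations, and because the SAP elsewhere says when a display is by time point.
- **Visibility of the relation.** A reader might infer that such plots cannot show it. They can: in the simulation a 4 h plot keeps most of it, and pooling weakens it without removing it.
- **One CrCl value per subject.** This is not stated. SAP 8.2 schedules chemistry at Screening and on Days -3, -1, 2, 7 and 28, so more than one value is possible.
- **Mixing of cohorts.** A reader might take the plots to cover all cohorts together. SAP 4 separates outputs by Part and sets default treatment groups for summaries. Only mixing of PB2452 and placebo within a Part remains open, and the SAP neither plans nor excludes it.
- **False positives.** In the simulation, a p-value computed on pooled points would reject in about 17% to 25% of runs with no true correlation. No p-value is planned for CrCl, so this is not a fault of the plan.
- **Importance.** The objective is exploratory, and the PK and urine parameters are listed by subject, so a later plot stays possible.

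The reply does not meet the main point. The SAP names a specific display, against concentrations and without a coefficient. Carried out exactly, it would still not yield the correlation that the objective asks for.

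**Conclusion.** The point holds as a mismatch between an exploratory objective and its only planned analysis. This is more than missing detail, because the method named is weaker than one available from parameters that the SAP already derives.

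The size depends on how the sentence is carried out. With plots by time point, little of the relation is lost, but there is still no coefficient and no link to exposure or renal clearance. With pooled times, the simulation suggests that the apparent correlation falls to less than half of its per-subject value. That figure rests on assumed half-lives and variances and on a model without a PB2452 effect. The confounding by treatment rests on the Phase 1 findings summarised in the protocol, and it applies only if PB2452 and placebo points are not told apart. Severity is low: a worthwhile improvement with no bearing on the primary or secondary analyses.

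**What to change.** In SAP 11.1, replace or supplement the CrCl sentence as follows:

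1. State the CrCl formula and the pre-dose creatinine used. Under the general Baseline rule in SAP 4 this would be the last non-missing pre-dose value, normally Day -1. That sample is drawn after ticagrelor starts on Day -2, so the choice should be explicit.
2. Plot baseline CrCl against ticagrelor and TAM AUC0-24, Cmax and CLR24, one point per subject, separately by Part, with points marked by treatment and cohort.
3. Report Spearman's coefficient with a 95% CI, labelled descriptive, for PB2452-treated subjects within each Part.
4. Show placebo subjects as plotted points only, because 4 to 6 in Part A and at most 3 in Part B cannot support a useful interval.

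The cost is a change of SAP wording and a few more exploratory outputs. No new data or PK parameters are needed. The downside is that the coefficients will be imprecise, and the report should say so.
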